Data analysis	
Approximately 669 patients will be randomized in 1:1:1 ratio in either of the three arms Fevipirant 450 mg dose, Fevipirant 150 mg dose or placebo in addition to standard of care. The randomization will be stratified according to patients peripheral blood eosinophil count (< 250 cells/μl or ≥ 250 cells/μl).
 
Primary analysis:
 
The primary endpoint of the study is total systemic corticosteroid dose in mg prednisone/prednisolone or equivalent over 52 weeks of treatment. The primary endpoint will be analyzed in subpopulation of patients with eosinophil count ≥ 250 cells/μl and in overall population.
 
Demonstration of total systemic corticosteroid SCS dose used in mg over 52 weeks of treatment for subpopulation of patients with eosinophil count ≥ 250 cells/μl and in overall population will be evaluated using the following primary null hypothesis:
 
 H₀₁ 450 eosinophil subgroup: the distribution of the total SCS dose (in mg) in Fevipirant 450 mg QD plus SoC is equivalent to the distribution of the total SCS dose (in mg) in placebo plus SoC in patients with eosinophil count ≥ 250 cells/μl H₀₂ 150 eosinophil subgroup: the distribution of the total SCS dose (in mg) in Fevipirant 150 mg QD plus SoC is equivalent to the distribution of the total SCS dose (in mg) in placebo plus SoC in patients with eosinophil count ≥ 250 cells/μl H₀₃ 450 overall population: the distribution of the total SCS dose (in mg) in Fevipirant 450 mg QD plus SoC is equivalent to the distribution of the total SCS dose (in mg) in placebo plus SoC for the overall population

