3.1 Study design

This study uses a randomized, multicenter, double-blind, double-dummy, placebo-controlled, parallel-group study design to determine the ability of fevipiprant plus SoC compared with placebo plus SoC to reduce the use of SCS in patients with severe asthma. The study will include:

- a Screening period of up to 2 weeks to assess eligibility;
- a Run-in period of 4 or 10* weeks to evaluate maintenance of asthma control and to collect baseline safety data. Upon completion of the Run-in period, all patients who met eligibility criteria will be randomized to 1 of 3 treatment groups (Fevipiprant 150 mg or 450 mg or placebo once daily) in a ratio 1:1:1. Randomized patients will be stratified according to their peripheral blood eosinophil count (< 250 cells/μl or ≥ 250 cells/μl);
- a Treatment period of 52 weeks and
- a Follow-up period of 2 weeks following the last dose of study drug to collect additional data for safety variables.

Approximately 669 patients will be randomized into this study. Please refer to [Table 6-1](#) for clinical visit schedule and list of procedures to be conducted at each visit.

Figure 3-1 Study design

* 4 weeks run-in for patients coming with high-dose ICS/LABA and 10 weeks for patients switching from mid-dose to high-dose ICS/LABA as per protocol during the run-in period.

The study will allow for flexible therapy, meaning that patients can be escalated or de-escalated on their SoC therapy or add any other controller (this is explained in more detail in [Section 5.5.5](#))

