5.3 Treatment assignment and randomization

At randomization visit, all eligible subjects will be randomized via Interactive Response Technology (IRT) to one of the treatment arms. The investigator or his/her delegate will contact the IRT after confirming that the patient fulfills all the inclusion/exclusion criteria. The IRT will assign a randomization number to the patient, which will be used to link the patient to a

treatment arm and will specify unique medication numbers for the first packages of study drug to be dispensed to the patient. The randomization number will not be communicated to the caller.

The randomization numbers will be generated using the following procedure to ensure the treatment assignment is unbiased and concealed from subjects and investigator staff. A patient randomization list will be produced by the IRT provider using a validated system that automates the random assignment of patient numbers to randomization numbers. These randomization numbers are linked to the different treatment arms, which in turn are linked to medication numbers. A separate medication list will be produced by or under the responsibility of Novartis Global Clinical Supplies using a validated system that automates the random assignment of medication numbers to packs containing the investigational drug(s).

Randomization will be stratified by peripheral blood eosinophil counts at Run-in Visit (< 250 cells/ml or \geq 250 cells/ml).

The randomization scheme for subjects will be reviewed and approved by a member of the Randomization Group.

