5.5.4 Instructions for prescribing and taking study treatment

Study treatment will be double-blind, double-dummy, and placebo-controlled during the treatment period. QAW039 will be supplied as tablets. Since the tablets for QAW039 150 mg and QAW039 450 mg are not identical, treatment will be double-dummy and patients will take 2 tablets of study medication (one tablet of blinded QAW039 at 150 mg dosage strength to be given together with one tablet blinded placebo to QAW039 450 mg or one tablet of blinded QAW039 at 450 mg dosage strength to be given together with one tablet blinded placebo to

QAW039 150 mg or one tablet blinded placebo to QAW039 150 mg and one tablet blinded placebo to QAW039 450 mg) once daily as described below.

During the run-in period all eligible patients will start:

Salmeterol/fluticasone 50/500 µg b.i.d. delivered by DPI (dry-powder inhaler) is marketed as Seretide® Accuhaler® or Seretide® Diskus® depending on the countries +/- tiotropium (or any LAMA approved for asthma) and/or LTRAs.

If a patient experiences an asthma exacerbation during the run-in period, the patient is considered run-in failure and can be re-screened only once 6 weeks after full recovery from the exacerbation.

At Randomization Visit, patients will be stratified according to their peripheral blood eosinophil counts at Run-In Visit (< 250 cells/ml or ≥ 250 cells/ml). Each randomized patient will then enter a 52-week treatment period where they will receive one of the following 3 treatments: (i) QAW039 150 mg once daily or (ii) QAW039 450 mg once daily or (iii) placebo once daily given on top of their individual background asthma treatment. All patients in this study will continue to receive their asthma medications as background treatment. The investigational treatment will be dispensed in medication packs (bottles) at dispensation visit during the treatment period to cover the treatment period between patient visits and to allow for late visits and other unforeseen events. All dosages prescribed and dispensed to the patient and all dose changes during the study must be recorded on the appropriate CRF.

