The total systemic corticosteroid dose in mg prednisone/prednisolone (or equivalent) over 52 weeks of treatment will be analyzed using the Wilcoxon-Mann-Whitney rank sum test (Van Elteren test). For overall population analysis will be stratified by randomization stratum – blood eosinophils levels (≥ 250 cells/ μl and < 250 cells/ μl). For subgroup with blood eosinophils ≥ 250 cells/ μl , analysis will not include stratification factor. The summary statistics for total SCS dose by treatment group will be provided.

The details and justification of primary as well as supplementary estimands are detailed in Estimand charter or statistical analysis plan (SAP).

The primary estimand will quantify the treatment effect based on on-treatment data. The total SCS dose data will be aggregated into monthly data for analysis. The primary estimand will account for different post-randomization events as follows:

- Use of rescue medications: Efficacy data collected during use of rescue medication will be used for analysis.

- Early discontinuation of study treatment (prior to completing 52 weeks of treatment period): For the patients discontinuing treatment early, the total SCS dose for 52 weeks will be obtained as annualized SCS dose. For example if patient took 280 mg for 7 months then for 12 months patient will be taking $280 \times 12/7 = 480$ mg total SCS dose.
- Use of biologics prior to discontinuation of treatment: Efficacy data collected during the use of biologics will be set to missing, since use of biologics can confound efficacy data. After replacing SCS dose with missing patient will not have data available for 12 months, thus total SCS dose will be obtained as annualized dose.

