2.2 Analysis sets

The screened set (SCR) will include all patients who provided informed consent.

The randomized set (RAN) will include all patients that were randomized. Data from these patients will be analyzed according to the treatment to which the patient was assigned at randomization.

The full analysis set (FAS) will include all randomized patients who received at least one dose of study treatment. It was considered reasonable to limit the FAS to patients who took study treatment, because the decision on whether or not treatment is started will not be influenced by the treatment group assignment due to the effective treatment blinding procedures described in protocol Section 5.4. Following the intent-to-treat principle, patients will be analyzed according to the treatment they were assigned to at randomization.

The safety set (SAF) will include all patients who received at least one dose of study treatment. Patients will be analyzed according to the treatment they received.

The analysis of the primary objective will be performed on the FAS. The FAS will be used for the analysis of all other efficacy variables. The SAF will be used in the analysis of all safety variables.

If an incorrect randomization stratum is inadvertently selected for a patient by the investigator in the IRT, patients will still be included in all analyses. The corrected stratum information as per the CRF data will be used in any analysis models.

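### Protocol Sections 5.3 and 5.5.4 print the randomisation cut-off as 250 cells/ml, contradicting the 250 cells/µl used everywhere else by a factor of 1000

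*Protocol*

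**What the plan says.** Two sections of the Protocol describe stratification at the point of randomisation, and both give the cut-off per millilitre:

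- Section 5.3: "Randomization will be stratified by peripheral blood eosinophil counts at Run-in Visit (< 250 cells/ml or" at or above the same number, in the same unit.
- Section 5.5.4: "patients will be stratified according to their peripheral blood eosinophil counts at Run-In Visit (< 250 cells/ml or ≥ 250 cells/ml".

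Two other descriptions of the same stratification give it per microlitre:

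- Protocol summary, data analysis: "The randomization will be stratified according to patients peripheral blood eosinophil count (< 250 cells/μl or" the complementary stratum.
- Section 3.1: "Randomized patients will be stratified according to their peripheral blood eosinophil count (< 250 cells/μl or" the complementary stratum.

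The analysis text also uses microlitres. Section 9.4.2 states each subgroup hypothesis with a cut-off of 250 cells/µl. For the overall population it says "For overall population analysis will be stratified by randomization stratum – blood eosinophils levels", followed by the two levels in cells/µl. Protocol Sections 1.2, 2.1, 3.2, 3.5 and 9.8 agree, as do SAP Sections 1.1, 1.2, 2.5.2 and 3. Nothing explains the different unit, and the list of changes in Amendment 1 does not mention it.

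**The concern.** The cut-off is a decision threshold. It determines the stratum in which a patient is randomised, and it separates the high-eosinophil patients, whose two hypotheses receive all of the initial alpha, from the rest. Section 5.3 describes the IRT procedure, and Section 5.5.4 tells sites how patients are stratified at the Randomization Visit. SAP Section 2.2 shows that a person may enter the stratum by hand: it provides for the case "If an incorrect randomization stratum is inadvertently selected for a patient by the investigator in the IRT". Someone who builds the system, or enters a stratum, from Sections 5.3 or 5.5.4 alone would be working from a figure 1000 times too low.

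What is at stake is the balance of the three arms within the high-eosinophil subgroup, which stratification is there to secure.

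**Working it through.** **Unit conversion.** 1 ml = 1000 µl, so:

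- as printed in Sections 5.3 and 5.5.4: 250 cells/ml ÷ 1000 = 0.25 cells/µl;
- as printed elsewhere: 250 cells/µl × 1000 = 250,000 cells/ml;
- ratio: 250,000 / 250 = 1000.

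**Could the printed cut-off separate patients?** The documents give no eosinophil distribution. They do give a scale: exclusion criterion 17 removes patients with a total white count below 2500 cells/µl. Against that minimum, 0.25 / 2500 = 0.01%, while 250 / 2500 = 10%. A threshold at 0.01% of the lowest admissible white count can be expected to put practically every patient in the upper stratum. That expectation is an assumption.

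**Planned split.** Protocol Section 9.8 has 134 high-eosinophil patients per arm out of 201, so 134 / 201 = 66.7%. Of 669 randomised patients:

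- as planned: 669 × 134/201 = 446 high and 223 low;
- Section 5.3 read literally: close to 669 high and close to 0 low.

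**What losing stratification would do.** Assume 223 patients per arm, 446 high-eosinophil patients in all, and allocation that ignores eosinophils. The expected number of high-eosinophil patients per arm is 223 × 2/3 = 148.7. The hypergeometric variance is 223 × (2/3) × (1/3) × (669 − 223)/(669 − 1) = 33.1, so the SD is 5.75. About 95% of allocations would give an arm between 148.7 − 1.96 × 5.75 = 137 and 148.7 + 1.96 × 5.75 = 160. Balance would be left to chance, but the comparison would still be randomised and unbiased.

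**Does the sample size depend on the wrong unit?** The plan's figure can be reproduced from the tie-adjusted Wilcoxon-Mann-Whitney formula in Section 9.8, with t = 0.5, two-sided alpha 0.025, power 0.90 and the six dose categories of the selected scenario:

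- (2.2414 + 1.2816)² = 12.411;
- 1 − Σ(mean category proportion)³ = 0.8578;
- the bracketed term in the denominator = −0.11506, and 12 × 0.25 × 0.11506² = 0.03971;
- N = 12.411 × 0.8578 / 0.03971 = 268.1 for two arms, or 134.0 per arm (stated: 134).

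Three arms give 402 in the subgroup and 3 × 201 = 603 overall. 603 / 0.9 = 670, or 223 × 3 = 669 when 201 / 0.9 is rounded to 223 per arm (stated: 669). The five alternative scenarios compute to 95.9%, 100%, 84.7%, 75.2% and 82.0% power, against stated values of 96%, 100%, 85%, 75% and 82%. The eosinophil cut-off does not enter the formula, and the section labels the subgroup in cells/µl. Correcting the unit changes none of these figures.

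**The case against.** The strongest reply is that this is an obvious typing error that no competent reader would apply. The right unit appears in the summary's own randomisation sentence, in Section 3.1 and throughout the analysis text. A cut-off that leaves one stratum empty could hardly survive set-up of a two-level stratification. The IRT and laboratory specifications are not among the documents, and nothing shows that either used millilitres. Most of this stands: it was probably never implemented literally. It does not remove the contradiction, and a randomisation specification should not depend on the reader guessing the intended unit.

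A second reply is that the µ was lost in PDF conversion. That cannot be wholly excluded, but it is unlikely. The unit appears as ml four times in two separate sections, and Section 5.5.4 prints µg correctly. A look at the source pages settles it.

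A third reply is that the SAP uses corrected stratum information from the CRF in its models when the IRT stratum was wrong. That protects the analysis labels, but it cannot restore stratified allocation after patients have been randomised.

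A reader might also infer that the printed unit puts everyone in the high subgroup, so that H01 and H02 become the same hypotheses as H03 and H04 and the van Elteren test loses its strata. The documents do not support this. The hypotheses and the primary model in Protocol Section 9.4.2 and SAP Section 2.5.2 state their own cut-off in cells/µl and do not take it from Section 5.3.

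**Conclusion.** The inconsistency is real and Sections 5.3 and 5.5.4 are wrong as written, by exactly a factor of 1000. The consequence is limited to allocation. If those sections were followed literally, and if practically all patients exceed 0.25 cells/µl, the lower stratum would be almost empty instead of holding about 223 of 669 patients. Balance between arms within the high-eosinophil subgroup would then be left to chance. The definition of the primary subgroup, the analysis strata, the alpha allocation, the power and the sample size are all unaffected. The documents do not show which unit the IRT used, so they do not establish that any patient was stratified wrongly.

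**What to change.** Change cells/ml to cells/µl for both strata in Protocol Sections 5.3 and 5.5.4. Confirm that the IRT specification used 250 cells/µl, and that the central-laboratory data transfer used the same unit (equivalently 0.25 × 10⁹/L).

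SAP Section 4 says the sponsor terminated the study early. If an amendment is no longer possible, state in the study report which unit the IRT applied and record the erratum. If the IRT did use millilitres, the report should also say that allocation was in effect unstratified and give the number of high-eosinophil patients per arm.

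The cost is a unit correction in two sentences and one check of a specification. No intended design feature or planned figure changes.

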5.4 Treatment blinding

This study consists of a double-blind, double-dummy, randomized treatment period.

[figure not shown]
Subjects, investigator staff, persons performing the assessments, and data analysts will remain blind to the identity of the treatment from the time of randomization until database lock, using the following methods: (1) Randomization data are kept strictly confidential until the time of unblinding, and will not be accessible by anyone else involved in the study. (2) For each dose level of QAW039, the identity of the treatment will be concealed by the use of matching placebo identical in packaging, labeling, schedule of administration, appearance, taste, and odor to QAW039.

A double-dummy design is used because the identity of the study drug cannot be disguised, as the drug products are visibly different in size.

Unblinding will only occur in the case of patient emergencies (see [Section 5.5.9](#)) and at the conclusion of the study.

Table 5-1 Blinding levels

Role	Time or Event		
	Randomization list generated	Treatment allocation & dosing	Safety event (single subject unblinded)
Subjects/Patients	B	B	B
Site staff	B	B	B
Unblinded site staff (see text for details)	B	B	B
Drug Supply and Randomization Office	UI	UI	UI
Unblinded sponsor staff (see text for details)	B	B	B
Statistician/statistical programmer/data analysts	B	B	B

Role	Time or Event		
	Randomization list generated	Treatment allocation & dosing	Safety event (single subject unblinded)
Independent committees used for assessing interim results	NA	NA	NA
All other sponsor staff not identified above	B	B	B
B Remains blinded NA Not applicable UI Allowed to be unblinded on individual patient level			

5.5 Treating the patient

Sponsor qualified medical personnel will be readily available to advise on trial related medical questions or problems.

5.5.1 Patient numbering

Each patient is uniquely identified by a Subject Number which is composed by the site number assigned by Novartis and a sequential number assigned by the investigator. Once assigned to a patient, the Subject Number will not be reused.

Upon signing the informed consent form, the patient is assigned the next sequential number by the investigator. The investigator or his/her staff will contact the IRT and provide the requested identifying information for the patient to register them into the IRT. The site must select the case report form (CRF) book with a matching Subject Number from the electronic data capture (EDC) system to enter data.

If the patient fails to be treated for any reason, the IRT must be notified within 2 days that the patient was not treated. The reason for not being treated will be entered on the Screening period Study Disposition CRF.

5.5.2 Dispensing the study drug

[figure not shown]
Each study site will be supplied with study drug in packaging of identical appearance.

The study drug packaging has a 2-part label. A unique medication number is printed on each part of this label which corresponds to one of the 3 treatment arms. Investigator staff will identify the study drug package(s) to dispense to the patient by contacting the IRT and obtaining the medication number(s). Immediately before dispensing the package to the patient, investigator staff will detach the outer part of the label from the packaging and affix it to the source document (Drug Label Form) for that patient's unique subject number.

5.5.3 Handling of study and additional treatment

5.5.3.1 Handling of study treatment

Study treatment must be received by a designated person at the study site, handled and stored safely and properly, and kept in a secured location to which only the investigator and designees have access. Upon receipt, all study treatment must be stored according to the instructions specified on the labels. Clinical supplies are to be dispensed only in accordance with the

protocol. Technical complaints are to be reported to the respective Novartis Country Organization Quality Assurance.

Medication labels will be in the local language and comply with the legal requirements of each country. They will include storage conditions for the study treatment but no information about the patient except for the medication number.

The investigator must maintain an accurate record of the shipment and dispensing of study treatment in a drug accountability log. Monitoring of drug accountability will be performed by monitors during site visits or remotely and at the completion of the trial. Patients will be asked to return all unused study treatment and packaging at the end of the study or at the time of discontinuation of study treatment.

At the conclusion of the study, and as appropriate during the course of the study, the investigator will return all unused study treatment, packaging, drug labels, and a copy of the completed drug accountability log to the Novartis monitor or to the Novartis address provided in the investigator folder at each site.

5.5.3.2 Handling of additional treatment

The following non-study treatment and rescue medication has to be monitored:

- salmeterol /fluticasone 50/500 µg b.i.d. or 50/250 µg b.i.d via Diskus[®]/Accuhaler[®] used as SoC
- prednisone/prednisolone (or equivalent) tablets (oral corticosteroids) used as rescue or preventive medication
- SABA (such as salbutamol 100 mcg or albuterol 90 mcg)
- tiotropium or "any LAMA approved for asthma"
- LTRA (if started prior of study entry)

The non-investigational treatment must be received by a designated person at the study site, handled and stored safely and properly, and kept in a secured location to which only the investigator and designees have access. Clinical supplies are to be dispensed only in accordance with the protocol.

The investigator must maintain an accurate record of the shipment and dispensing of the non-investigational treatment in a drug accountability log. Monitoring of drug accountability will be performed by monitors during site visits or remotely and at the completion of the trial. Patients will be asked to return all unused non-study treatments and packaging at the end of the study or at the time of discontinuation from the study.

